### 6.6.3 Sensitivity Analysis

The MMRM method used for the analysis will be applied to the mITT population with the observed data without imputation. The following sensitivity analyses will also be considered to explore the impact of missing data on the conclusion of the primary analysis.

The first sensitivity analysis is using a multiple imputation method based on the monotonic missing pattern under the assumption of MAR. The intermittent missing data will be imputed using multiple imputation MCMC procedure.

The second sensitivity analysis is also using multiple imputation, however, under the assumption of MNAR to explore the validity of MAR using pattern-mixture model:

1) For subjects who discontinue study participation prior to Week 56 and do not have follow-up visit, the missing data will be imputed using the observed data from the subjects in the same arm who discontinue the study treatment but have the primary endpoint measurement in the follow up visit using a regression method. The

intermittent missing data will be imputed using multiple imputation MCMC procedure. An ANCOVA model using a similar mixed procedure (without the repeated measures) as the primary analysis will be applied to these multiple-imputed % change in BMI at Week 56 with treatment, baseline BMI value as a covariate, and age and gender as stratification factors. The results of ANCOVA analysis on the multiple imputed datasets will be combined and summarized.

2) Tipping point analyses: An additional sensitivity analysis using a 2-way tipping-point strategy will be conducted on the primary endpoint to explore the influence of missing data from active treatment and placebo arms on the overall conclusion from statistical inference. In this approach, a wide spectrum of assumptions regarding the magnitude of missingness (from less conservative to more conservative) is proposed for replacing missing data. All subjects who drop out the study will have their unobserved efficacy data imputed by the observed data from completers in the same arm using the multiple imputation method based on the monotonic missing pattern under the assumption of MAR with the resulting imputed values further worsened by an amount  $\delta$ . Scenarios where dropouts on active arms have worse outcomes than dropouts on placebo will be included. The analysis finds a 'tipping' point from among these assumptions under which the study conclusions shift from being favorable to the active treatments to being unfavorable. After such a tipping point is determined, clinical judgment can be applied as to the plausibility of the assumptions underlying this tipping point. The tipping point can be identified while the result is no longer statistically significant.

The third sensitivity analysis is the LOCF. For those subjects who discontinue study participation prior to Week 56, the last observed weight and height will be used to derive the change in BMI.

Similar analyses will be performed for the primary endpoint for the mITT population.

#### **6.6.4 Subgroup Analysis**

BMI change will be tabulated by age and gender. Additionally, further exploratory subgroup analyses of the primary efficacy endpoints may include evaluation by race and/or other subgroups deemed medically and/or scientifically important.

#### **6.6.5 Exploratory Analysis**

IWQOL-Kids will be analyzed by a similar MMRM model as for the primary endpoint where the baseline BMI value will be replaced by the baseline value of the corresponding endpoint as a covariate to evaluate effects of treatment on Impact of Weight on Quality of Life-Kids (IWQOL-Kids) questionnaire scores.

Change from baseline will be presented for various glycemic, lipid markers and BMI Z-score parameters with numerical measures using descriptive statistics. BMI Z-score will be calculated as  $[(\text{BMI}/\text{M})^L - 1]/(\text{L} * \text{S})$  where L, M and S values are available in percentile data files.

## 6.7 Safety

All safety analyses will be done for the Safety population. Safety data will be summarized for all treatment groups.

Safety will be assessed by an evaluation of adverse events (each study visit); laboratory parameters (screening, periodically during the study and end of study); electrocardiograms; physical examinations (screening, end of study); PHQ-9: Modified for Teens, C-SSRS, and vital signs (at each study visit). Descriptive statistics will be generated for the questionnaire data.

### 6.7.1 CANTAB

Cognitive testing will include CANTAB Paired Associates Learning (PAL), Pattern Recognition Memory (PRM) and Spatial Span (SSP) and will be collected at Screening, Baseline, Week 16 and Week 56 for each treatment assignment. The tasks will evaluate effects on episodic memory, visual pattern recognition memory and working memory capacity, respectively. The key outcome measures to be included in the analysis are described in Table 2.

For each key CANTAB outcome measure, descriptive summary statistics (n, mean, median, standard deviation, minimum and maximum) for change from baseline will be reported for visits at Week 16 and Week 56 across all treatment groups (Placebo, Mid-dose and Top-dose of VI-0521) and stratification factors for age and gender. Line graphs of mean change from baseline to Week 16 and Week 56 by treatment groups and stratification factors will also be produced.

Mixed effects models with repeated measures will be used to generate least squares means and standard errors for change from baseline to Weeks 16 and 56 for each treatment group, controlling for stratification factors age and gender and baseline performance for each CANTAB outcome measure.

The standardized mean difference (effect size) between placebo and each treatment group will be calculated using the least squares mean change from baseline to Week 16 and Week 56 estimates and the pooled standard deviation of change across both treatment and placebo groups.

**Table 2 CANTAB Key outcome measures**

CANTAB Task	Key Outcome Measure (code)	Description	Cognitive Domain / Direction of Effect
PAL	Total Errors Adjusted (PALTEA)	The number of times the subject chose the incorrect box for a stimulus on assessment problems, plus an adjustment for the estimated number of errors they would have made on any problems, attempts and recalls they did not reach. This measure allows you to compare performance on errors made across all subjects regardless of those who terminated early versus those completing the final stage of the task	Episodic memory/ Lower is better
PAL	First Attempt Memory Score (PALFAMS)	The number of times a subject chose the correct box on their first attempt when recalling the pattern locations. Calculated across all assessed trials	Episodic memory/ Higher is better
PRM	Percent Correct Immediate (PRMPCI)	The number of correct patterns selected by the subject in the immediate forced-choice condition, expressed as a percentage	Visual pattern recognition memory/ Higher is better
PRM	Percent Correct Delayed (PRMPCD)	The number of correct patterns selected by the subject in the delayed forced-choice condition, expressed as a percentage	Visual pattern recognition memory/ Higher is better
SSP	Forward Span Length (SSPFSL)	The longest sequence of boxes successfully recalled by the subject. Applicable to Forward variants only	Working Memory Capacity/ Higher is better
SSP	Reverse Span Length (SSPRSL)	The longest sequence of boxes successfully recalled by the subject. Applicable to Reverse variants only	Working Memory Capacity/

**6.7.2 PHQ-9**

The PHQ-9 questionnaire will be completed at every study visit.

The mean change in PHQ-9 score from baseline to Week 56, along with the percentage of subjects with at least 1 PHQ-9 score indicative of depression of moderate or greater severity (PHQ-9 score of 10 or more), the percentage of subjects with at least 1 PHQ-9 score indicative of major depression (Kroenke), and the percentage of subjects with at least 1 positive answer to question 9 relating to suicidal ideation will be presented by treatment group. A listing of all subjects presenting with any of the outcomes listed above, or a PHQ-9 score of 15 or more will be provided.

### 6.7.3 C-SSRS

For each item of the C-SSRS, counts and percentages will be presented by treatment group and in total summarizing the number of yes responses at each study visit. In addition, a composite measure will be summarized at each study visit that includes the following C-SSRS items: Active suicidal ideation with some intent to act without specific plan, Active suicidal ideal with specific plan and intent, Actual attempt, Engaged in non-suicidal non-injurious behavior, Interrupted attempt, Aborted attempt, Preparatory acts or behavior, and Suicidal behavior. The baseline distribution of responses to the C-SSRS will also be presented.

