10.14 Columbia Suicide Severity Rating Scale (C-SSRS)

The Columbia Suicide Severity Rating Scale is an 11-item clinician-administered assessment of both suicidal behavior (6 items) and suicidal ideation (5 items).¹⁰ Each of the items comprising this scale corresponds to a specific level, or severity of ideation or behavior, and is answered on a yes/no basis. This assessment will be administered to all subjects at screening in order to confirm the absence of suicidal behavior or ideation with at least some intent to act on it, and to document the pre-study status of all subjects included in the treatment program. Subsequently,

C-SSRS evaluations may be done at the investigator's discretion to evaluate and aid in diagnosis of reported or suspected events of suicidality. All C-SSRS assessments must be administered by a trained staff member. If any test reveals suicidal behavior or ideation with some intent to act on it, then test results must be confirmed by a physician investigator prior to discharging the subject from the study visit (see [Appendix 5](#)).

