Actual Attempt: 
A potentially self-injurious act committed with at least some wish to die, as a result of act. Behavior was in part thought of as method to kill oneself. Intent does not have to be 100%. If there is any intent/desire to die associated with the act, then it can be considered an actual suicide attempt. There does not have to be any injury or harm, just the potential for injury or harm. If person pulls trigger while gun is in mouth but gun is broken so no injury results, this is considered an attempt.
 
Inferring Intent: Even if an individual denies intent/wish to die, it may be inferred clinically from the behavior or circumstances. For example, a highly lethal act that is clearly not an accident so no other intent but suicide can be inferred (e.g. gunshot to head, jumping from window of a high floor/story). Also, if someone denies intent to die, but they thought that what they did could be lethal, intent may be inferred.
 
Have you made a suicide attempt? Have you done anything to harm yourself? Have you done anything dangerous where you could have died?
 
What did you do? Did you _____ as a way to end your life? Did you want to die (even a little) when you _____? Were you trying to end your life when you _____? Or did you think it was possible you could have died from _____? Or did you do it purely for other reasons / without ANY intention of killing yourself (like to relieve stress, feel better, get sympathy, or get something else to happen)? (Self-Injurious Behavior without suicidal intent)
 
If yes, describe:
 
Has subject engaged in Non-Suicidal Self-Injurious Behavior?
		Yes  No  Total # of attempts _____

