Interrupted Attempt: 
When the person is interrupted (by an outside circumstance) from starting the potentially self-injurious act (if not for that, actual attempt would have occurred).
 
Overdose: Person has pills in hand but is stopped from ingesting. Once they ingest any pills, this becomes an attempt rather than an interrupted attempt. Shooting: Person has gun pointed toward self, gun is taken away by someone else, or is somehow prevented from pulling trigger. Once they pull the trigger, even if the gun fails to fire, it is an attempt. Jumping: Person is poised to jump, is grabbed and taken down from ledge. Hanging: Person has noose around neck but has not yet started to hang - is stopped from doing so.
 
Has there been a time when you started to do something to end your life but someone or something stopped you before you actually did anything?
 
If yes, describe:
		Yes  No  Total # of interrupted _____
Aborted Attempt: 
When person begins to take steps toward making a suicide attempt, but stops themselves before they actually have engaged in any self-destructive behavior. Examples are similar to interrupted attempts, except that the individual stops him/herself, instead of being stopped by something else.
 
Has there been a time when you started to do something to try to end your life but you stopped yourself before you actually did anything?
 
If yes, describe:
		Yes  No  Total # of aborted _____

Preparatory Acts or Behavior: Acts or preparation towards imminently making a suicide attempt. This can include anything beyond a verbalization or thought, such as assembling a specific method (e.g. buying pills, purchasing a gun) or preparing for one's death by suicide (e.g. giving things away, writing a suicide note).
 
Have you taken any steps towards making a suicide attempt or preparing to kill yourself (such as collecting pills, getting a gun, giving valuables away or writing a suicide note)?
 
If yes, describe:
	
Yes No
 
 

Suicidal Behavior: Suicidal behavior was present during the assessment period?
	
Yes No
 
 

Completed Suicide:
	
Yes No
 
 

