
around neck but has not yet started to hang - is stopped from doing so.
 
Has there been a time when you started to do something to end your life but someone or something stopped you before you actually did anything?
 
If yes, describe:
	
Total # of interrupted
 <hr/>

Aborted Attempt:
 
When person begins to take steps toward making a suicide attempt, but stops themselves before they actually have engaged in any self-destructive behavior. Examples are similar to interrupted attempts, except that the individual stops him/herself, instead of being stopped by something else.
 
Has there been a time when you started to do something to try to end your life but you stopped yourself before you actually did anything?
 
If yes, describe:
	
Yes No
 
 
 
Total # of aborted
 <hr/>

Preparatory Acts or Behavior:
 
Acts or preparation towards imminently making a suicide attempt. This can include anything beyond a verbalization or thought, such as assembling a specific method (e.g. buying pills, purchasing a gun) or preparing for one's death by suicide (e.g. giving things away, writing a suicide note).
 
Have you taken any steps towards making a suicide attempt or preparing to kill yourself (such as collecting pills, getting a gun, giving valuables away or writing a suicide note)?
 
If yes, describe:
	
Yes No
 
 

Suicidal Behavior:
 
Suicidal behavior was present during the assessment period?
	
Yes No
 
 

Completed Suicide:
	
Yes No
 
 

Answer for Actual Attempts Only	Most Recent Attempt Date:	Worst/Most Lethal Attempt Date:	Initial/First Attempt Date:

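### The C-SSRS composite in SAP 6.7.3 can be inflated by non-suicidal self-injury, an item that it also misnames

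*SAP*

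**What the plan says.** SAP 6.7.3 first promises counts and percentages of yes responses for every C-SSRS item, by treatment group and visit. It then adds that "a composite measure will be summarized at each study visit that includes the following C-SSRS items". The list opens with "Active suicidal ideation with some intent to act without specific plan, Active suicidal ideal with specific plan and intent, Actual attempt" and continues with "Engaged in non-suicidal non-injurious behavior, Interrupted attempt, Aborted attempt, Preparatory acts or behavior, and Suicidal behavior", which makes eight items. The SAP does not name what the composite measures. It also does not say whether a subject is a case on any yes response or whether yes responses are counted.

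Both versions of the form in Protocol Appendix 5 (baseline and since last visit) carry the row "Has subject engaged in Non-Suicidal Self-Injurious Behavior". The probe above it glosses the behavior as "Self-Injurious Behavior without suicidal intent". Both versions also have a general row asking whether "Suicidal behavior was present during the assessment period" and a row "Completed Suicide". Only the last of these is absent from the composite list.

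Protocol 10.14 describes the scale as an "11-item clinician-administered assessment of both suicidal behavior (6 items) and suicidal ideation (5 items").

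**The concern.** Suicidality is scheduled for assessment at every visit in adolescents, and safety is a primary objective. The composite is the only C-SSRS output that counts subjects across items, so it is the figure most likely to be quoted.

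The list has two defects. Read literally, one entry matches no field on the form. Read as evidently intended, that entry is behavior that the form separates from suicidal behavior by the absence of intent. The composite leaves out ideation items 1 to 3, including active suicidal thoughts without intent, yet it counts self-injury without suicidal intent. If true suicidal events are few, a handful of self-injury reports could make up much of the composite in any arm.

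**Working it through.** The documents state no figure for this composite, so there is none to reproduce. The check compares item content and then sizes the effect.

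**1. The protocol's concept.** Exclusion criterion 13 (Section 7.2), the screening purpose in Section 10.14 and the event handling in Section 11.1.4 all combine suicidal behavior with ideation carrying intent to act. None of them names non-suicidal self-injury.

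**2. Items side by side.**

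| Row on the Appendix 5 form | Within the protocol's concept | In the SAP composite |
|---|---|---|
| Ideation 1 to 3 | no | no |
| Ideation 4 (some intent) | yes | yes |
| Ideation 5 (plan and intent) | yes | yes |
| Actual attempt | yes | yes |
| Non-suicidal self-injury | no | yes (misnamed) |
| Interrupted attempt | yes | yes |
| Aborted attempt | yes | yes |
| Preparatory acts | yes | yes |
| Suicidal-behavior flag | yes | yes |
| Completed suicide | yes | not listed |

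Each list has 8 items and they share 7. One item is in the composite without belonging to the concept, and one is not listed.

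**3. Does the stated item count settle what was meant?** Section 10.14 gives 5 ideation + 6 behavior = 11. The form has 5 ideation rows and, with self-injury counted, 7 behavior rows. Dropping any one behavior row gives 6, so the count does not show which list was intended.

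**4. Baseline.** The baseline form asks about lifetime behavior. Criterion 13 excludes a history of suicidal behavior or of ideation with intent, which covers the seven matching items. It does not name past non-suicidal self-injury. In correctly enrolled subjects, that is essentially the only composite item left that can be positive.

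**5. Size per subject.** With planned arms of 50, 50 and 100, one subject positive only on self-injury adds 1/50 = 2 percentage points or 1/100 = 1 point. This holds for any binary outcome in these arms.

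**6. Illustration with assumed rates.** The documents give no rate for self-injury or suicidality. Suppose a proportion p reports self-injury only. The expected extra positives are n × p, and the chance of at least one is 1 − (1 − p)^n.

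| n | p | Expected extra | Chance of at least one |
|---|---|---|---|
| 50 | 1% | 0.5 | 40% |
| 50 | 5% | 2.5 | 92% |
| 100 | 1% | 1 | 63% |
| 100 | 5% | 5 | 99% |

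Now let s be the rate of true suicidality and p the rate of self-injury, independent of it. With an any-yes rule, the share of composite positives that are non-suicidal is 1 − s/(s + p − sp).

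- s = 2%, p = 1%: 1 − 0.02/0.0298 = 33%.
- s = 0.5%, p = 5%: 1 − 0.005/0.05475 = 91%.

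The range is wide because both rates are assumed.

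**7. Why the combination rule matters.** A subject with one actual attempt would normally be yes on that row and on the general flag. That is one case under an any-yes rule but two if yes responses are counted.

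**The case against.** **The SAP names no construct, so the benchmark is the reader's.** This is true of the SAP text. Section 11.1.4 is also a rule for handling events and not an analysis definition. But the SAP keeps ideation items 4 and 5 and drops 1 to 3, which is the same intent threshold the protocol uses three times. If a broader self-harm measure was intended, the SAP should say so.

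**The misnaming is a slip.** Probably so. The same sentence writes ideal for ideation, and only one form row fits. Correcting the name, however, still leaves a non-suicidal item in the composite.

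**The per-item tables already show self-injury.** They do, and a reader can see how often it was reported. They cannot yield the number of subjects with any suicidal event, because one subject can be positive on several rows. That number would have to be worked out from the subject listings.

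**Completed suicide.** Because it is not listed, a reader might infer that a completed suicide would not be counted. The documents do not support that. The form's lethality scale, answered for actual attempts only, includes a code for death, and actual attempt is in the composite. The general suicidal-behavior flag is there too. Completed suicide is also tabulated as its own item, and SAP 6.7.6 lists adverse events resulting in death.

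**Impact.** SAP 6.7 calls for descriptive statistics on questionnaire data, and no test or model is specified for the composite. This stands and limits the weight of the point.

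**Conclusion.** The composite includes one item that does not fit the protocol's concept of suicidality, and names it wrongly. It can therefore be inflated by non-suicidal self-injury, most visibly at baseline. A reader might go further and conclude that the composite does not measure suicidal behavior or ideation with intent. That is not supported, since seven of its eight items measure exactly that.

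Each subject positive only on self-injury adds 2 points in an arm of 50 or 1 point in the arm of 100. How many such subjects there would be cannot be derived from the documents.

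The conclusion rests on three assumptions: that the misnamed entry means the self-injury row; that the composite is meant to follow the protocol's intent threshold; and that any yes makes a case. The baseline point also assumes criterion 13 is applied as written. An investigator could still exclude a subject with past self-injury under the general criterion 27. The change is worth making because it alters the count at almost no cost, but it concerns a descriptive safety table only.

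**What to change.** Revise SAP 6.7.3 as follows:

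- Remove the non-suicidal item from the composite. Report it on its own line by arm and visit, under the form's name.
- Name the construct as suicidal behavior or ideation with intent to act.
- Define a case as any yes on ideation item 4 or 5, actual, interrupted or aborted attempt, preparatory acts, or the suicidal-behavior flag. Keep the flag, since nothing in the documents argues for dropping it.
- Add completed suicide for completeness, although it is probably already captured through actual attempt or the flag.

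The cost is one SAP sentence and one derived flag. The self-injury line already exists among the per-item tables and needs only the right label. No data collection, visit or clinical rule changes.

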### 6.7.4 Hand and Wrist X-Ray

Changes of bone age from baseline to Week 56 in hand and wrist X-ray will be evaluated. Differences between treatment groups will be evaluated using methods similar to those used to evaluate other continuous variables.

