7.3 Subject Withdrawal

Subjects are free to withdraw from the clinical trial or discontinue treatment at any time for any reason.

The sponsor reserves the right to discontinue this trial at any time (see Section 13.0 on clinical trial discontinuation criteria).

Subject participation in this clinical trial may be discontinued for any of the following reasons:

- Occurrence of any medical condition or circumstance that exposes the subject to substantial risk and/or does not allow the subject to adhere to the requirements of the protocol;
- Any serious adverse event (SAE), clinically significant adverse event (AE), severe laboratory abnormality, intercurrent illness, or other medical condition that indicates to the Investigator that continued participation is not in the best interest of the subject;
- Subject's (or a parent's or legal guardian's) decision to withdraw;
- Requires other medical treatment that is excluded by the protocol (see Section 8.5);

- Subject failure to comply with protocol requirements or study related procedures; or
- Termination of the clinical trial by the sponsor, FDA, or other regulatory authorities.

Withdrawn subjects will not be replaced.

Subjects discontinued from treatment should be encouraged to remain in the trial off-treatment and to continue study visits at the scheduled intervals. Subjects who withdraw completely from the trial at any point should complete the end of study (Visit 16, Week 56) procedures. The date of last dose should be recorded.

Every effort should be made to document subject outcome. For subjects who elect to withdraw from the trial without continuing study visits, the investigator should inquire about the reason for withdrawal, request that the subject return all unused investigational product(s), request that the subject return for a final visit (Section 9.1.4) and follow-up with the subject regarding any unresolved adverse events.

At about the 56-week time point, withdrawn subjects who have not continued study visits should be asked to return to the site to obtain weight and height measurements at a minimum and, if possible, all the other tests and procedures (except physical examination and ECG) required for end of study visit.

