9.1.4 Treatment Week 56, End of Study; Early Termination (Visit 16)

The end of study visit will be performed for subjects completing the study or for subjects who are withdrawn from the study prior to completion of the study at the time of their treatment termination. For subjects who withdraw from the study prior to completion, the site will also attempt to contact the subject at or about the 56-week time point to obtain end of study assessments.

Activities at the end of study visit include:

- Administer PHQ-9, C-SSRS, and IWQOL-Kids questionnaires;
- Administer neurocognitive battery (CANTAB);
- Obtain vital signs;
- Obtain weight and waist circumference measurements;
- Measure height and calculate BMI;
- Collect study drug from previous visit, assess treatment compliance, and perform drug accountability;
- Obtain blood sample for chemistry, hematology, and lipids, panel;
- Obtain blood sample for HbA1c;
- Obtain urine sample for routine urinalysis and urine pregnancy test (female only);
- Administer glucose load for OGTT and obtain blood sample for glucose and insulin at 2 hours following oral glucose load (Section 10.10);
- Perform complete physical examination (include Tanner Staging);
- Perform and evaluate 12-lead electrocardiogram (ECG);
- Conduct hand and wrist X-ray;
- Conduct DXA measurement (if applicable);
- Record any changes in concomitant medications;
- Record any adverse events reported or observed;
- Discontinue subject's study participation.

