10.7 X-Ray of the Hand and Wrist

An X-ray of the hand and wrist will be performed at baseline, and end of study or early termination visit to assess bone growth. Equipment and procedures used to obtain hand and wrist X-ray data will be standardized as described in a separate document. X-rays will be read at a central facility and the reader will be blinded.

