### 3.4 Safety Endpoints

Safety will be assessed by evaluating adverse events (AEs)/serious adverse events (SAEs); vital signs, laboratory parameters (screening, periodically during the study and end of study); electrocardiograms; physical examinations; cognitive function tests using the Cambridge Neuropsychological Test Automated Battery (CANTAB). All subjects will be screened for the presence and severity of depression using the PHQ-

9: Modified for Teens and for suicidal/ideation using the Columbia Suicide Severity Rating Scale (C-SSRS) and follow up assessments will be done at each visit after treatment has been initiated. Bone age (X-ray of the hand and wrist) will be evaluated at baseline and end of study or early termination. Effect on bone mineral density and bone mineral content, as evaluated by Dual-energy X-Ray Absorptiometry (DXA) will be performed at baseline, end of study or early termination, at selected sites.

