## 5. DATA Handling

### 5.1 Time Points and Visit Windows

Day 0 (Visit 2) is defined as the Baseline/Randomization visit, is also the first day of treatment. Relative days are calculated as (assessment date – Day 1 date). The day prior to Day 0 is Day -1.

The following visit windows defined in Table 1 will be used for the by-visit analyses of the primary endpoint, the secondary and other endpoints. All other analyses will use the nominal study visit as defined in the Study Schedule and eCRF.

If there are multiple visits (scheduled or unscheduled) within a visit window, the measurement closest to the target day of the visit will be used in the analysis. If the measurements are equally distant to the target day, then the later one will be used in the analysis. If both scheduled and unscheduled visits fall within the same visit window, the scheduled visit will be used for analysis.

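### SAP 6.7.4 analyses bone-age change to Week 56 without saying whether early-termination films count as Week 56, and without adjusting for time between films

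*SAP*

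**What the plan says.** SAP 6.7.4 defines the analysis in two sentences. The first is "Changes of bone age from baseline to Week 56 in hand and wrist X-ray will be evaluated". The second is "Differences between treatment groups will be evaluated using methods similar to those used to evaluate other continuous variables".

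The film schedule is in SAP 3.4: "Bone age (X-ray of the hand and wrist) will be evaluated at baseline and end of study or early termination". Protocol 10.7 and Appendix 1 agree, so each subject has one scheduled post-baseline film, at Visit 16. Protocol 9.1.4 places that visit at completion or, "for subjects who are withdrawn from the study prior to completion of the study at the time of their treatment termination", which can be any week. SAP Table 1 gives Visit 16 the single label Week 56/ET and an analysis window of Day 378 to Day 398.

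SAP 5.1 applies the Table 1 windows to by-visit analyses of the primary, secondary and other endpoints. It then adds: "All other analyses will use the nominal study visit as defined in the Study Schedule and eCRF". Bone age is not named under either rule.

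Under Protocol 7.3, withdrawn subjects who have stopped attending are asked back at about Week 56 for weight and height and, if possible, "all the other tests and procedures (except physical examination and ECG) required for end of study visit". The X-ray is therefore included. SAP 5.2 states that safety data are analysed as observed, without imputation.

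**The concern.** Bone age advances with time, so a change measured over a few weeks is not comparable with one measured over 56 weeks. If both carry the same visit label, the arm mean depends on how many subjects left and when, as well as on skeletal maturation.

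The methods that 6.7.4 borrows do not correct for this. The efficacy model in SAP 6.6.1 and 6.6.2 has treatment, visit, their interaction, the baseline value, age stratum and gender. It has no term for time between films or age at the film. The stratum (12-14 or 15-16 years) is fixed at baseline and cannot adjust for a short interval.

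Protocol 8.4.4 names effects on growth as a safety concern. Bone age is the one skeletal measure for which the SAP plans a between-group comparison: DXA in 6.7.5 is descriptive, and height is not in the vital-signs summary in 6.7.8. With the visit rule open, two programmers following the same text could produce different results.

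**Working it through.** The plan gives no expected change, standard deviation or power for bone age, so it has no figure of its own to reproduce.

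**Inputs**
- Full interval: 56 weeks (SAP 6.7.4).
- *d*, share of subjects whose only post-baseline film is at ET: 10% (assumed) and 30% (the dropout figure in Protocol 12.2 and SAP 2.3, used here as an upper-range value).
- *t*, mean week of the ET film: 12, 28 or 44 (assumed).
- *r*, bone-age years per calendar year: 1 (assumed; lower near skeletal maturity).

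**1. Nominal-visit reading, mean within one arm**

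True change = r × 56/52 = 1.077 years.
Pooled mean = r × [(1 − d) × 56/52 + d × t/52].
Shortfall = r × d × (56 − t)/52. As a proportion it is d × (56 − t)/56, which does not depend on r.

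| d | t (week) | Pooled mean (years) | Shortfall (years) | Shortfall (%) |
|---|---|---|---|---|
| 10% | 12 | 0.992 | 0.085 | 7.9 |
| 10% | 28 | 1.023 | 0.054 | 5.0 |
| 10% | 44 | 1.054 | 0.023 | 2.1 |
| 30% | 12 | 0.823 | 0.254 | 23.6 |
| 30% | 28 | 0.915 | 0.162 | 15.0 |
| 30% | 44 | 1.008 | 0.069 | 6.4 |

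**2. Nominal-visit reading, difference between arms**

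With no true effect, top-dose minus placebo = r × (d_placebo − d_top) × (56 − t)/52.

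- Placebo 40%, top-dose 25% (mid-dose 30%, so 30% overall): 0.15 × 44/52 = 0.127; 0.15 × 28/52 = 0.081; 0.15 × 12/52 = 0.035 years for t = 12, 28, 44.
- Placebo 20%, top-dose 35%: the same sizes with the sign reversed.
- If r were 0.5, these sizes would halve, to about 0.02 to 0.06 years.

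With equal dropout there is no spurious difference, but a true difference in rate is diluted by (0.7 × 56 + 0.3 × t)/56. That leaves 76%, 85% or 94% of it at t = 12, 28, 44 with d = 30%.

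For scale, take a two-sided 5% normal test with 50 placebo and 100 top-dose subjects. Add d(1 − d) × ((56 − t)/52)² to each arm's variance for the mixed intervals. The 15-point gap at t = 28 then gives a false-positive rate of about 13%, 9% or 7% for an assumed SD of 0.5, 0.75 or 1.0 year. Across t = 12 to 44, and both directions of the gap, the range is about 5.5% to 22%.

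**3. Window reading**

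ET films at Weeks 12, 28 and 44 are at Days 84, 196 and 308. Table 1 puts these in the Week 12, 28 and 44 windows, so none enters Day 378 to 398 and the shortfall is zero. Those subjects have no Week 56 value unless they return, and none is imputed. The Week 56 result then describes completers and returners, which 6.7.4 does not say.

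**4. Two films in one subject**

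A subject with an ET film and a later recall film has two Visit 16 films. Under windows they fall in different windows and do not conflict. Under nominal visits, 6.7.4 does not say which one counts; the tie rules in SAP 5.1 are written for measurements within a window.

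**The case against.** The strongest objection is that the SAP already excludes early films. Bone age is a listed endpoint in SAP 3.4, it is analysed at a named visit, and 5.1 extends the windows to other endpoints. The Table 1 row that carries the ET label itself has a day range. On that reading there is no pooling and no two-film conflict.

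Nor does the explicit windowing of laboratory values in 6.7.7 show that unmentioned endpoints use nominal visits. Its stated purpose is to bring in unscheduled visits, and 6.7.8 handles vital signs differently again.

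The size is also open to challenge. The 30% is a planning figure for the BMI power calculation. The protocol encourages subjects who stop drug to stay in the study, and it recalls those who withdraw, so the share with only an ET film could be well below 30%. The ET timing, maturation rate, SD and dropout gap have no source in the documents.

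Most of this stands. A reader might infer that the plan does analyse ET films as Week 56 values and so understates skeletal maturation, or that placebo dropout will hide slowing on drug. The documents support neither. The pooling depends on one of two tenable readings, and nothing indicates which arm would lose more subjects or lose them earlier.

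What the objection does not remove is the open choice. Section 6.7.4 does not override the nominal-visit rule in 5.1, and no adjustment for elapsed time is stated under either reading.

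**Conclusion.** The point holds as an unresolved choice in a planned between-group safety comparison, not as a demonstrated bias. If nominal visits are used, short-interval and 56-week changes are mixed. The mean is then low by about 2 to 8% at a 10% ET-only share, or about 6 to 24% at 30%, and a 15-point gap between arms gives a spurious difference of about 0.04 to 0.13 years in either direction. If windows are used, the understatement is zero and the issue becomes selection of completers and returners.

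The sizes in years rest on an assumed one bone-age year per calendar year and shrink in proportion if maturation is slower. The percentages do not depend on the rate, but they do depend on the assumed ET share and timing. The measure is skeletal maturation, so the result should not be read as height growth. The point merits a change because the remedy is cheap and gives a better analysis whichever rule was intended.

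**What to change.** In SAP 6.7.4:

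- Take the Week 56 result only from films in Day 378 to 398, including subjects who stopped treatment or withdrew and returned. Since the recall is timed only as about Week 56, also say how a film after Day 398 is handled.
- Analyse the change in bone age minus chronological age at the film date. This removes the expected one-for-one advance, but some dependence on elapsed time remains if the rate is not 1, so the window is still needed. Advance per elapsed year is not a substitute: it is a different quantity and very noisy over short intervals.
- Summarise earlier ET films separately, with their elapsed time.

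In SAP 6.7.5, apply the same date window to any raw BMD or BMC summary. Age-referenced Z-scores are less exposed.

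The cost is SAP wording; it uses film dates and ages, with no new data collection. The downside is fewer subjects in the Week 56 bone tables. Those subjects will be completers and returners only, and the SAP and the tables should say so.
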